#### 8.4. Deaths and Serious Adverse Events

Serious adverse events (SAEs) will be listed and summarized in a similar manner as described in Section 8.3. Separate displays listing and summarizing death, including time to death and cause of death, will also be created if a death occurs.

# 8.5. Clinical Laboratory Evaluation

Clinical laboratory measurements include serum chemistry, urinalysis, and hematology. Results will be converted to standardized units where possible. Chemistry and hematology panels are run by a central lab; as such, normal ranges will come from the central lab.

Laboratory data will be plotted to show patterns over time. Summary statistics including 25th percentile, median, and 75th percentile will be plotted for each visit by treatment group. Lines connecting individual subject results from subjects with grade 2 or higher values will be overlaid on each figure. For lab results that are not gradable, results from subjects with values outside of 2 \*ULN or 0.5\*LLN will be overlaid. Tests with qualitative results (such as "present" or "positive") will not be plotted.

# 8.6. Vital Signs, Physical Findings, and Other Observations Related to Safety

# 8.6.1. Vital Signs

Vital sign information will be collected on the Vital Signs CRF page at every study visit. Data listings sorted by treatment group, subject, vital sign parameter, and time of assessment will be provided for vital signs measurements.

#### 8.6.2. Physical Examinations

Physical exam information will be collected on the Physical Exam CRF page at every study visit. Data listings will be provided for physical examination results and sorted by treatment group, subject, body system, and time of assessment.

#### 9. PHARMACOKINETIC EVALUATION

No pharmacokinetic evaluations will be performed for ALE06.

Version: 1.0 Page 33 of 48

#### 10. OTHER ANALYSES

#### 10.1. Use of Medications

Medications will be coded according to the World Health Organization (WHO) Drug Dictionary (version 2013.03). Medications reported on the CRF will be categorized for analysis as prior, concomitant, or after study treatment by comparing the medication start and stop dates with the first and last dose of study medication dates. Prior medications will have both the medication start and stop dates prior to the first dose of study medication date. After medications will have both the medication start and stop dates after the last dose of study medication date. All other medications will be classified as concomitant, indicating that use of the medication overlapped with use of the study medication by at least one day.

The number and percentage of subjects receiving prior, concomitant, and after medications will be presented overall and by medication class. When reporting the number of subjects receiving the medication, a subject will only be counted once if they ever received the medication within the medication class. Percentages will be based on the number of subjects in the analysis population.

Version: 1.0 Page 34 of 48

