#### 6.2. Treatment Adherence

Subjects will be randomized to one of the two study treatment arms below.

- MMF maintenance arm: These subjects will continue MMF treatment (1000-3000 mg/day) for the rest of their study participation (up to Week 60).
  - Baseline MMF dose = 3000 mg/day
    - Up to 60 weeks on 3000mg/day MMF
  - Baseline MMF dose = 2500 mg/day to 2750 mg/day
    - Up to 60 weeks on 2500mg/day MMF
  - Baseline MMF dose = 2000 mg/day to 2250 mg/day
    - Up to 60 weeks on 2000mg/day MMF
  - Baseline MMF dose = 1500 mg/day to 1750 mg/day
    - Up to 60 weeks on 1500mg/day MMF
  - Baseline MMF dose = 1000 mg/day to 1250 mg/day
    - Up to 60 weeks on 1000mg/day MMF
- MMF withdrawal arm: These subjects will taper off MMF over 12 weeks and remain off MMF for the rest of their study participation (up to Week 60 or until the primary endpoint of disease reactivation is met, whichever comes first).
  - Baseline MMF dose = 3000 mg/day
    - Four weeks on 1000 mg MMF twice a day (BID)
    - Four weeks on 1000mg (morning) & 500mg MMF (evening) QD
    - Four weeks on 500 mg MMF BID
    - Up to 48 weeks on no MMF
  - Baseline MMF dose = 2500 mg/day to 2750 mg/day
    - Four weeks on 1000mg MMF BID
    - Four weeks on 1000mg (morning) & 500mg (evening) MMF QD
    - Four weeks on 500 mg MMF BID
    - Up to 48 weeks on no MMF
  - Baseline MMF dose = 2000 mg/day to 2250 mg/day
    - Four weeks on 1000mg (morning) & 500mg (evening) MMF QD
    - Four weeks on 500mg MMF BID
    - Four weeks on 500 mg MMF QD
    - Up to 48 weeks on no MMF
  - Baseline MMF dose = 1500 mg/day to 1750 mg/day
    - Four weeks on 500mg MMF BID
    - Four weeks on 500 mg MMF BID
    - Four weeks on 500 mg MMF QD
    - Up to 48 weeks on no MMF
  - Baseline MMF dose = 1000 mg/day to 1250 mg/day

Version: 1.0 Page 14 of 48

- Four weeks on 500 mg MMF BID
- Four weeks on 500 mg MMF QD
- Four weeks on 500 mg MMF QD
- Up to 48 weeks on no MMF

Prescribed MMF doses for subjects in the study will be collected on the Study Drug Dose Log CRF page. Information on this page includes dates of dose changes, prescribed doses (including a "zero" dose when a subject completes tapering), and reasons for dose changes. Bottles of MMF dispensed along with pill counts will be collected on the Study Drug Accounting Log CRF page. This page includes information on the number of bottles dispensed, number of pills in the bottle, dates dispensed and returned, pills returned, and pills lost.

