#### 8.2. Extent of Exposure

Extent of exposure during the trial will be described for MMF. Exposure will be measured as the total number of days on medication defined as last dose date – first dose date + 1 and the cumulative dose of that medication defined as the sum of the doses in mg taken up to the relevant cutoff date. Exposure will be summarized until a subject stops taking study provided MMF.

Version: 1.0 Page 30 of 48

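### SAP 10.1 sorts medications by each subject's last study-MMF dose, so use in Weeks 12 to 60 is labelled differently by arm and the descriptive medication percentages are not comparable

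*SAP*

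**What the plan says.** SAP 10.1 (Use of Medications) classifies each record by "comparing the medication start and stop dates with the first and last dose of study medication dates". A record is prior if it both started and stopped before the first dose. For the class at the other end, "After medications will have both the medication start and stop dates after the last dose of study medication date". For the remainder, "All other medications will be classified as concomitant", which the SAP explains as an overlap with study drug of at least one day. Subjects are counted once per medication class, and "Percentages will be based on the number of subjects in the analysis population". The section makes no allowance for how long each subject was on study drug.

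The dates that drive the rule are set by randomization. SAP 6.2 (Treatment Adherence) says of the withdrawal arm: "These subjects will taper off MMF over 12 weeks and remain off MMF for the rest of their study participation". Each taper schedule there ends with "Up to 48 weeks on no MMF". The maintenance arm stays on MMF up to Week 60. SAP 8.2 ties exposure to trial-supplied drug only: "Exposure will be summarized until a subject stops taking study provided MMF". Footnote 12 of the schedule of events adds that the trial supplies no further MMF once the primary endpoint is met, so MMF resumed for a reactivation does not move the last study dose later.

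SAP 10.1 mentions presentation overall and by medication class, without naming arms. Display by arm follows from the general convention in Protocol 8.3. SAP section 12 lists no change on this point.

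**The concern.** The boundary between concomitant and after is a consequence of the assigned arm. A steroid burst or an antibiotic course given in, say, Week 30 and finished by Week 32 goes into the after rows for a withdrawal subject and into the concomitant rows for a maintenance subject still taking study drug. Because the denominator is every subject in the analysis population, the percentages do not correct for the unequal windows.

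A reader who compares the concomitant rows across arms would see less medication use after withdrawal where there may be no difference. This applies to drugs given for flares and also to anti-infectives. Protocol 1.5 suggests that stopping MMF may lower infection risk, so a lower anti-infective percentage in the withdrawal arm could be mistaken for that benefit. A reader who compares the after rows would see the opposite distortion. Needed medications form part of a secondary objective (Protocol 2.2.1), so these tables are likely to be read for that purpose even though they are not the formal endpoints.

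**Working it through.** **The plan's own figure.** Each withdrawal schedule has three steps of four weeks: 3 × 4 = 12 weeks on study drug. With follow-up to Week 60, 60 − 12 = 48 weeks off drug, which matches SAP 6.2. The compliance calculation in the same section also uses 12 weeks for the withdrawal arm and 60 for the maintenance arm.

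**Windows for a newly started medication.**
- Withdrawal arm: at most about 12 weeks in which a new start can be concomitant.
- Maintenance arm: at most 60 weeks.
- Ratio of maximum windows: 60 / 12 = 5. Share of follow-up in which a short course gets a different label: 48 / 60 = 80%.

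**Effect on the tabulated percentages.** The table counts subjects with at least one record in a class, so the ratio of windows is not the ratio of percentages. To see the size, assume that new short courses start at the same constant rate L per subject per 60 weeks in both arms, that each course has a recorded stop date, and that all subjects complete 60 weeks. The documents give no such rate, so L is an assumption, taken from 0.25 to 3.

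- Concomitant, maintenance: 1 − exp(−L)
- Concomitant, withdrawal: 1 − exp(−L × 12/60)
- After, withdrawal: 1 − exp(−L × 48/60)
- After, maintenance: about 0 while study drug continues to Week 60

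| L (assumed) | Concomitant, maintenance | Concomitant, withdrawal | After, withdrawal |
|---|---|---|---|
| 0.25 | 22.1% | 4.9% | 18.1% |
| 0.5 | 39.3% | 9.5% | 33.0% |
| 1 | 63.2% | 18.1% | 55.1% |
| 2 | 86.5% | 33.0% | 79.8% |
| 3 | 95.0% | 45.1% | 90.9% |

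True use is identical in every row. The ratio of the two concomitant percentages runs from about 4.5 (22.1 / 4.9) down to about 2.1 (95.0 / 45.1).

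**Early stopping in the maintenance arm.** Suppose 10% of maintenance subjects stop study drug at Week 30 (an assumption). At L = 1, concomitant becomes 0.9 × 63.2% + 0.1 × (1 − exp(−0.5)) = 60.8%, and after becomes 0.1 × (1 − exp(−0.5)) = 3.9%. The gap from the withdrawal arm's 18.1% and 55.1% remains.

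**With one common window.** Counting all use from Day 0 to Week 60 in both arms gives 1 − exp(−L) in each, so 63.2% and 63.2% at L = 1.

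**Ongoing records.** A drug started after the last dose and still running at study exit has no stop date. It does not meet the after rule, so by the letter it falls into the remainder and becomes concomitant, although it never overlapped study drug as the SAP's explanation requires. The section does not settle which reading applies.

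**The case against.** The strongest reply is that little depends on this table. The analyses that address needed medications use windows defined alike in both arms:
- The primary endpoint draws on steroid and immunosuppressant records flagged as prescribed after Day 0 for SLE activity, and on the flare and endpoint form (SAP 7.2.1).
- Aggressive adjunctive or cytotoxic therapy counts throughout participation and expressly includes withdrawal subjects already off MMF (SAP 7.3.8).
- Cumulative and excess steroid dose run over 60 weeks or to early termination (SAP 7.3.9). The recovery endpoints run from reactivation to return to the pre-flare dose or the end of follow-up (SAP 7.3.13.3 and 7.3.13.4).
- Reasons for new or increased major immunosuppressives have their own summaries (SAP 7.3.2).

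All of that stands, and it limits the point to descriptive tables. It also rules out three stronger readings that a reader might infer.

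One is that most flare treatment in the withdrawal arm is hidden. It is not: SAP 10.1 tabulates the after class too. Treatment begun during the taper stays concomitant, long-running treatment without a stop date may also be concomitant, and maintenance subjects whose study drug stops at reactivation (Protocol 5.10.1) acquire after records as well.

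Another is that the rule understates the cost of withdrawal. No defined endpoint uses these labels, so this is not shown.

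The third is that a five-fold difference is built into the table. Five is the ratio of maximum windows for new starts. The percentages differ by less, and drugs continued from baseline, such as the required anti-malarials or baseline prednisone, are concomitant in both arms.

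It can also be said that study-drug dates usefully separate use on drug from use off drug. That is a fair aim, but the separation coincides with the arms and so cannot support a comparison between them. Finally, SAP 10.1 does not itself specify display by arm. A pooled table, however, would combine two different windows under one label.

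**Conclusion.** The point holds as a defect of labelling in the descriptive medication tables. For medications started and stopped in Weeks 12 to 60, the class depends on the randomized arm, and the maximum window for newly started concomitant medications is about 12 against 60 weeks. By-class percentages shown by arm are therefore not comparable even with the same true use. The size in percentage terms depends on how often new courses start, which the documents do not state. Under equal use, short courses with stop dates and complete follow-up, the concomitant percentage in maintenance would be roughly 2.1 to 4.5 times that in withdrawal over the assumed range. Ongoing records, drugs carried over from baseline and early stopping in the maintenance arm reduce the contrast. No data are lost, and the primary, steroid-dose and adjunctive-therapy endpoints are unaffected. This is a minor point that is worth correcting because the correction is simple.

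**What to change.** In SAP 10.1, replace the study-drug anchors with dates common to both arms:
- Prior: stopped before Day 0.
- On-study (concomitant): any use from Day 0 to the last study visit.
- After: dropped, or begun only at study exit.
- Records still ongoing at study exit count as on-study use.
- State that the table is shown by arm and overall.
- Optionally, show Weeks 0 to 12 and 12 to 60 separately, with the same cut in both arms.

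The cost is SAP wording and table programming. No new data are needed. What is given up is that the default table no longer separates use on study drug from use off it, unless the Week 12 split is shown.

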# 11. INTERIM ANALYSES AND DATA MONITORING

The progress of the study will be monitored by the Data and Safety Monitoring Board (DSMB). The NIAID Autoimmune DSMB will be chartered to review safety data and to make recommendations regarding continuation, termination, or modification of the study. The DSMB will formally review the safety data at least yearly. The discontinuation of study treatment will also be periodically reported to the DSMB.

In addition, safety data will be reviewed by the DSMB when an event occurs that is of sufficient concern to the National Institute of Allergy and Infectious Diseases (NIAID) medical monitor or protocol chair to warrant review, or when an event occurs that could contribute to a predefined stopping rule specified in the protocol.

Findings will be reported to Institutional Review Boards (IRBs) and health authorities.

# 11.1. Interim Analysis

Interim study results will be reported to the DSMB for planned Data Review Meetings. Reports prepared for these meetings will focus on study conduct and subject safety and may include information on enrollment, randomization, site activation status, protocol deviations, subject status and demographics, and safety analyses. In particular, at each DSMB review, disease reactivation rates in each arm and the risk difference (i.e. risk\_MMFwithdrawal - risk\_MMF maintenance) will be reported along with the 2-sided 95% confidence interval. If the lower 95% confidence limit about the risk difference exceeds 0.40, the DSMB should consider whether or not the study should be stopped for safety concerns. In order to trigger the guidance, the number of disease reactivations in the MMF withdrawal arm must exceed the number in the MMF maintenance arm, but the magnitude of the excess depends on the sample size. Some examples of observed scenarios that would trigger the guidance are as follows:

# Subjects per arm	Minimum # excess reactivations in the MMF withdrawal arm*
10	7
20	13
30	18
40	23
50	27
60	32

\* The excess needed to trigger the guidance also depends on the # of reactivations in the MMF maintenance arm.

In addition, if  $\leq$  10% of the first 80 subjects experience disease reactivation after accruing 60 weeks of post-randomization time and the study is still accruing subjects, then the pooled estimate of the disease reactivation rate may be used to re-estimate the required sample size. The pooled observed rate (and the 2-sided 95% CI) will be used to reconsider the maximum potential difference between the arms. If power is at least 85% under scenarios where the assumed rate in the maintenance arm is  $\leq$  5% with an acceptable risk difference of 0.15, then the study team may consider reducing the sample size.

Version: 1.0 Page 35 of 48

#### 12. CHANGES TO THE ANALYSES PLANNED IN THE PROTOCOL

[figure not shown]
- Section 7.2. Primary Endpoint. Statistical methods to obtain effect estimates and confidence intervals for the probability of observing clinically significant disease reactivation by 60 weeks have been changed from exact methods for complete data (proportions with Clopper Pearson intervals) to Kaplan-Meier predict-limit estimators to allow for censoring of subjects who terminated early without evidence of disease reactivation.
- 2. Section 7.3.3. Time to First SELENA-SLEDAI Flare: Time to first SELENA-SLEDAI flare has been changed from using withdrawal date to using Day 0 date. This allows us to calculate time to first SELENA-SLEDAI flare in both arms, since the Maintenance arm does not start withdrawal, and is consistent with the timing of the time to disease reactivation endpoint specified in Section 7.3.1.
- 3. Section 7.3.6. Probability of Experiencing a BILAG A or B Flare: This is a new endpoint was added to the SAP by the study team.
- 4. Section 11.1. Interim Analysis: The sample size re-estimation specified if ≤ 10% of the first 80 subjects experienced disease reactivation was not performed. We observed that after 60 weeks of post-randomization, 8 of the first 80 (10%) subjects experienced disease reactivation. Although the rate of disease reactivation was low, the team opted not to re-estimate the sample size. Rates of BILAG and SELENA-SLEDAI flares, which will also be important for evaluating the impact of MMF withdrawal, are higher than 10%. The larger sample size is necessary to improve precision for these important secondary endpoints and will strengthen the primary analysis.

Version: 1.0 Page 36 of 48

# 13. REFERENCES

# 14. APPENDICES

# 14.1. Study Flow Chart

Version: 1.0 Page 37 of 48

# 14.2. Schedule of Events

Table 6.1, Schedule of Events													A	s Need	led
Visit Name	Screen-	Base-	Week	Week	Week	Week	Week		Week		Week			End	Unsched
	ing	line	4	8	12	16	20	24	32	40	48	60 	Flare 	End- point 	
Unless otherwise noted, all assessments are to be done by unblinded personnel.		IIIIC	M1	M2	M3	M4	M5	M6	M8	M10	M12	M15		point	-uicu
Visit Window (days)	-28 to -1	0	± 7	± 7	± 7	± 7	± 7	± 7	± 7	± 7	± 7	± 7	n/a	n/a	n/a
Central Clinical Draw (mL, approximate)	18.5	10	10	10	13	10	10	13	13	13	13	13	13	13	0
Central Research Draw (mL)	0	55	23.5	23.5	23.5	23.5	55	23.5	23.5	23.5	23.5	55	55	23.5	0
Visit Draw Total (mL, approximate)	18.5	65	33.5	33.5	36.5	33.5	65	36.5	36.5	36.5	36.5	68	68	36.5	0
	Physician	n Requ	irement	S				•							
REMS Program Enrollment	X														
	General	Asses	sment												
Randomization		X													
Informed Consent	X														
Demographics	X														
Medical History, including Family History of Autoimmune Disease	X														
Physical Examination 	X	X	X	X	X	X	X	X	X	X	X	X	X	X	X
Physical Examination  by a blinded investigator				X	X	X	X	X17							
Vitals, including weight (& height at Screening)	X	X	X	X	X	X	X	X	X	X	X	X	X	X	X
Physician's Global Assessment (0-3 VAS)	X	X	X	X	X	X	X	X	X	X	X	X	X	X	
m-SLEDAI 	X														
SELENA-SLEDAI*13		X	X	X	X	X	X	X	X	X	X	X	X	X	
SELENA-SLEDAI* 13 & treatment questionnaire by a blinded investigator				X	X	X	X	X17							
SLICC/DI* 		X						X			X	X	X	X	
BILAG* 		X	X	X	X	X	X	X	X	X	X	X	X	X	
FACIT T		X						X			X	X	X	X	
SF-36 		X						X			X	X	X	X	
Lupus QoL (Control of the Control of		X						X			X	X	X	X	
Medications Assessment	X	X	X	X	X	X	X	X	X	X	X	X	X	X	X
Adverse Event Assessment		X	X	X	X	X	X	X	X	X	X	X	X	X	X
	Stu	ıdy Drı	ug					•							
T reatment Period 							60 weel	KS							
Dispense Study Drug		X	X	X	$X^{14}$	$X^{14}$	$X^{14}$	$X^{14}$	$X^{14}$	$X^{14}$	$X^{14}$				
Assess Study Drug Compliance			X	X	X	$X^{14}$	$X^{14}$	$X^{14}$	$X^{14}$	$X^{14}$	$X^{14}$	$X^{14}$			
Lo	cal Labora	tory A	ssessm	ents 											
Urinalysis: dipstick, microscopic, & spot protein-creatinine	X	X	X	X	X	X	X	X	X	X	X	X	X	X	
Pregnancy Test, if applicable 1	X				X			X		X		X			
PPD, if applicable 	X														
Central Laboratory Assessments 															
QuantiFERON®-TB Gold In-Tube Test (QFT-G_IT), if applicable (~3 mL)	X														
Infectious Disease Screen (~8.5 mL): HIV antibody, hepatitis B surface antigen, HCV	Х														
antibody with HCV RNA (PCR) if antibody positive 10	Λ														
Chemistries (~3 mL) – albumin, ALP, ALT, AST, BUN, creatinine, glucose, phosphorus,	Х				X			X	X	X	X	X	X	X	
potassium, bilirubin, total protein	Λ.		L		1		L	А	Λ	Λ.	Λ.	А	^	Λ	
Serum creatinine		$X^{19}$	X 	$X^{19}$		$X^{19}$	X 								

Table 6.1, Schedule of Events										As Needed						
Visit Name	Screen-	Base-	Week 4	Week 8	Week 12	Week 16	Week 20	Week 24	Week 32	Week 40	Week 48	1	Flare 	End-	Unsched	
Unless otherwise noted, all assessments are to be done by unblinded personnel.	ing	ing line	ing line	M1	M2	M3	M4	M5	M6	M8		_		po	point	int  -uled 
Visit Window (days)	-28 to -1	0	± 7	± 7	± 7	± 7	± 7	± 7	±7	± 7	± 7	± 7	n/a	n/a	n/a	
Anti-dsDNA,C3, C4 (~6 mL)		X19	X19	X19	X	X19	X19	X	X	X	X	X	X	X		
Hematologies (~4 mL): hemoglobin, MCV, platelet count, RDW, WBC, lymphocytes, monocytes, neutrophils	X	X	X	X	X	X	X	X	X	X	X	X	X	X		
Hematology (6 mL): lymphocyte subset, if applicable 	X															
Cer	ntral Mech	anistic	c Specii	nens												
Serum for Cytokine/Chemokines/Antibodies  to Sm, RNP, SSA/Ro, SSB/La (10 mL)		X18	X	X	X	X	X	X	X	X	X	X18	X18	X		
RNA Assays (5 mL)		X	X	X	X	X	X	X	X	X	X	X	X	X		
Future Use: PBMCs & Plasma (40 mL)		X					X					X13	X			
Future Use: Plasma (8.5 mL)			X	X	X	X		X	X	X	X	XIII		X10		
Future Use: Urine (10 mL)		X					X					$X^{20}$	$X^{z_1}$	X		

- 1. Week 60: should a subject withdraw early, he/she should complete all assessments listed under the Week 60 visit.
- 2. Flare visits: should occur when a subject experiences a flare and may coincide with a regularly scheduled study visit.
- 3. Endpoint visits: should occur when a subject reaches primary endpoint, as described in Section 3.2, Description of Primary Endpoint and may coincide with a regularly scheduled study visit.
- 4. Unscheduled visits: all noted assessments must be done, but any additional assessments that the investigator feels should be done should be collected. Note: if during the unscheduled visit, the investigator suspects a flare is occurring, the site must conduct a Flare Visit.
- 5. PPD or QuantiFERON®-TB Gold In-Tube Test (QFT-G-IT): unless performed within 12 weeks prior to screening and documented as negative in the subject's records, or unless subject is known to have a positive or indeterminate test and has documentation of appropriate therapy.
- 6. Physical examinations are to include, at least, the following systems: general appearance, skin, head/eyes/ears/nose/neck/throat, respiratory/chest, cardiovascular, abdominal, neurological, & musculoskeletal/extremities.
- 7. Subjective assessments must be done at the beginning of the visit, prior to any other study assessments (except for informed consent at Screening).
- 8. Local & Central Laboratory Assessments: see Section 6.3.6, Blood Draw Prioritization
- 9. Lymphocyte subset: only if the subject was on a B cell depleting agent in the past 3 years and the test was not done within 12 weeks prior to screening documenting detectable B cells
- 10. In fectious disease screen: unless documented as negative within 12 weeks prior to the Screening visit.
- 11. Pregnancy tests: for women on MMF and of childbearing potential only. Additional pregnancy tests should also be done when clinically indicated.
- 12. Treatment Period: will end if a subject meets primary endpoint. While visits & assessments will occur as scheduled, ALE06 will no longer provide any more MMF. Any treatment medications chosen by the investigator will be documented on the concomitant medications log.
- 13. ALE06 will typically use a spot urinalysis rather than a 24-hour urine assessment for the BILAG\*, mSLEDAI, SELENA-SLEDAI\*, and SLICC/DI\*. However, if indicated, results from a 24-hour urine collection may be used.
- 14. For subjects randomized to MMF maintenance arm only.
- 15. Future Use: PBMCs & Plasma will be drawn at Week 60 only if the subject did not experience a mild/moderate flare requiring an increase in prednisone or a severe flare requiring increased immunomodulatory medication while on study.
- 16. Future Use: Plasma will be drawn at Week 60 or Endpoint only if the subject did experience a flare while on study.
- 17. At Week 24, a blinded physical exam and SELENA-SLEDAI\* should only be conducted if the subject is being monitored for flare at the Week 20 visit.
- 18. Antibodies to Sm, RNP, SSA/Ro, and SSB/La will only be assessed at the Baseline, Week 60, and if needed, the flare visit.
- 19. Serum creatinine will be run off the Baseline, Weeks 4, 8, 16, and 20 Anti-dsDNA, C3, C4 blood draw.
- 20. FutureUse:Urine will be collected at Week 60 only if the subject did not experience a flare while on study.
- 21. FutureUse:Urine will be collected at any (and all) Flare Visits where increased predisone or immunomodulatory medication is prescribed

Version: 1.0 Page 39 of 48

